The proposed study will use parallel-groups, randomized, sham controlled, double-blinded design in which 36 participants with motor incomplete SCI (AIS B – D level) will randomly assigned to receive tDCS combined with repetitive arm training (RAT) or sham tDCS combined with R-A training. During the first 20-minute participants (n=24) in the experimental group will receive 20 minutes of anodal tDCS (2 mA) on motor cortex contralateral to their trained side followed by RAT for 60 minutes. Participants (n=12) in the control group will receive 20 minutes of sham tDCS followed by RAT for 60 minutes. In the sham stimulation 2 mA of anodal current will be delivered in a ramp up and down fashion for 30 seconds at the beginning and 30 seconds at the end of 20 minutes of stimulation. Treatment will be administered at an intensity of 5 sessions per week for 2 weeks.

The randomization schedule will be provided by project statistician ([name]).

Outcome measure:

Feasibility outcome measure: Adherence with therapy will be measured as;
(1) the number of treatment sessions attended by each participant,
(2) number of drop-outs in each group,
(3) participant's perceptions of the use of study implementation (using the tDCS and exercise equipment, numerical rating scale with 'not difficult at all' at 0, and 'very difficult' at 10)
(4) participant's perceptions of usefulness of the intervention (numerical rating scale with 'not at all useful' at 0 and 'very useful' at 10).

The telerehabilitation intervention will be considered as feasible if at least 80% adherence rate is achieved (completed number of sessions \geq 8 out of 10), if attrition rate is no higher than 10% in each study group, if at least 40 minutes of 60 minutes exercise session is completed and if no serious adverse events took place (other than expected side effects from tDCS).

Clinical outcome measure: Primary clinical outcome measure is GRASSP prehension performance (Kalsi-Ryan et al., 2012). Secondary clinical outcome measures are grip strength and Spinal Cord Injury Independence Measure (SCIM III) (Itzkovich, Gelernter et al. 2007). Assessments will be repeated immediately after completion of 10 sessions and at 4-weeks follow-up.

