Data for feasibility and adherence will be analyzed using descriptive statistics. For effectiveness, difference in GRASSP score in active arm and between active vs sham arm (immediately after treatment - baseline) will be analyzed with paired t test (if the normality is satisfactory with Kolmogrov-Smirnov test). If the K-S test suggests skewed distribution, we will conduct Wilcoxon signed rank test and Wilcoxon rank sum test for these two analyses.

In multivariable analysis, we will fit a mixed model for data collected at baseline and ten sessions and at 30-days follow-up in both study arms. Patient will be included as random effect of the mixed model. The fixed effects include treatment arm (active, sham) and time (0 for baseline, 1-10 for ten sessions). First, we will consider time levels as nominal and test interaction between treatment and time. The interaction will be added if it will be significant. Second, we hope to parametrically model time. The mean trajectory plot will guide us on the parametric form of time. Our emphasis will be linear time and 3rd-order polynomial time. We tend to favor the 3rd-order polynomial time as we believe that the GRASSP score will increase greatly for the first few sessions and then become stable.

In mixed model analysis, besides incorporating patient random effect, we will also test if there exists stronger correlation among measurements with shorter time intervals. We will specify a few serial correlation patterns including exponential, Toeplitz and banded Toeplitz. The random effect specification will be extended to incorporate random time slope. We will fit all these models and report AIC values to guide our decision on covariance pattern.

10. Potential Benefits

The results of these studies may benefit subsequent future subjects if remotely supervised, home-based combined tDCS and repetitive arm training proves to be effective when compared to repetitive arm training only.

The benefits of participating in this study may be improved arm and hand movement. However, there may be no benefit from participating in this study.

11. Risk-Benefit Ratio:

The potential improvement of arm and hand movement outweighs the risk of non-invasive brain stimulation, fatigue, pain and discomfort.

12. Consent Procedures:

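### The mixed-model covariance list in section 9 includes a redundant combination and cannot represent gains that differ between patients and are then held, so a model-based post-treatment contrast may be too liberal

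*Combined protocol and SAP*

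**What the plan says.** Section 9 (Data analysis) fits a mixed model with the patient as a random effect and arm and time as fixed effects. Time is first treated as nominal and the arm-by-time interaction is tested. On covariance it says: "In mixed model analysis, besides incorporating patient random effect, we will also test if there exists stronger correlation among measurements with shorter time intervals". Then: "We will specify a few serial correlation patterns including exponential, Toeplitz and banded Toeplitz". A random slope in time is a further extension, and the choice is made as follows: "We will fit all these models and report AIC values to guide our decision on covariance pattern". No unstructured or unequal-variance pattern, robust variance or degrees-of-freedom method is named.

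The same section describes the expected course of the outcome, as a reason to favour a cubic form for time: "we believe that the GRASSP score will increase greatly for the first few sessions and then become stable".

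The change in GRASSP from baseline to immediately after treatment is compared between arms in a separate analysis, by a t test or a Wilcoxon test.

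Section 4 (Study Design) fixes when the outcome is measured: "Assessments will be repeated immediately after completion of 10 sessions and at 4-weeks follow-up". The schedule of activities in section 6 agrees: GRASSP at baseline, post-treatment and follow-up, and at none of the ten sessions. Section 4 gives 36 participants, 24 active and 12 sham.

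**The concern.** A random intercept adds one constant to every variance and covariance. A Toeplitz matrix already has a free value at every lag, so the constant can be moved between the two terms without changing the fit. A model on the list is therefore over-parameterised.

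The second matter bears on inference. All treatment falls in the first, shorter interval. If some patients gain a lot and others little, and each then keeps what was gained, change from baseline to post-treatment varies widely between patients while change from post-treatment to follow-up varies little. The named patterns impose equality or the opposite ordering. The fitted model then pools the two intervals, making the standard error of the first change too small and that of the second too large. AIC can rank the listed patterns but cannot supply one that is absent. A tDCS effect read from the model at post-treatment could look more certain than the data allow, and could disagree with the change-score test with no stated rule for resolving it.

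**Working it through.** **Inputs.** From the documents: 24 and 12 participants (section 4), hence 36 − 2 = 34 degrees of freedom for a pooled between-arm comparison; three GRASSP visits (sections 4 and 6); the covariance list (section 9). Assumed, because not given: two-sided 5%, visits at 0, 2 and 6 weeks, complete data, no true arm effect, nominal time, Toeplitz applied by visit order, and all SDs and correlations. There is no stated figure to reproduce.

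**1. Identifiability.** Let J be the all-ones matrix and T_k the indicator of lag k. The covariance is σ_b²·J + Σθ_k·T_k, and J = ΣT_k. Adding d to σ_b² and subtracting d from every θ_k leaves it unchanged. Three visits: 1 + 3 = 4 parameters, rank 3. Twelve visits: 1 + 12 = 13 parameters, rank 12. At three visits, intercept plus two-band Toeplitz has rank 3 of 3 and spans the same matrices as Toeplitz, so two list entries are one model. At twelve visits the banded versions differ from full Toeplitz and are identifiable. The redundant model has the same fitted covariance and standard errors as plain Toeplitz.

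**2. What each pattern implies for the variance of change** (first interval 2 weeks, second 4 weeks):
- random intercept, Toeplitz or banded Toeplitz: equal in both intervals;
- exponential: larger over the longer, second interval;
- random slope in weeks, variance d, residual variance σ²: 2²d + 2σ² = 4d + 2σ² against 4²d + 2σ² = 16d + 2σ², again larger in the second.

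None permits a larger value in the first interval. A random slope can lower the baseline-to-post correlation, but only through spread that keeps growing, which makes the later change more variable.

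**3. Large-sample size of the error.** With SD 1 at each visit, the true variance of the first change is 2(1 − r_BP). Toeplitz replaces r_BP by the mean of r_BP and r_PF; a random intercept alone uses the mean of all three correlations. Type I error = 2Φ(−1.96·√(fitted/true)). Correlations are baseline-post / baseline-follow-up / post-follow-up.

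| Correlations | True | Toeplitz fitted | Ratio | Type I | Intercept fitted | Ratio | Type I |
|---|---|---|---|---|---|---|---|
| .7/.7/.95 | 0.60 | 0.35 | 0.583 | 13.4% | 0.433 | 0.722 | 9.6% |
| .8/.8/.95 | 0.40 | 0.25 | 0.625 | 12.1% | 0.30 | 0.75 | 9.0% |
| .8/.8/.9 | 0.40 | 0.30 | 0.75 | 9.0% | 0.333 | 0.833 | 7.4% |
| .9/.9/.95 | 0.20 | 0.15 | 0.75 | 9.0% | 0.167 | 0.833 | 7.4% |
| .8/.8/.8 | 0.40 | 0.40 | 1 | 5.0% | 0.40 | 1 | 5.0% |

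First row, Toeplitz: mean correlation (0.70 + 0.95)/2 = 0.825; 2(1 − 0.825) = 0.35; 0.35/0.60 = 0.583; √0.583 = 0.764; 1.96 × 0.764 = 1.497; 13.4%. In that row the later change has true variance 2(1 − 0.95) = 0.10 against the same fitted 0.35, so it is overstated 3.5-fold.

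**4. Simulation with AIC choice, 24 v 12, t on 34 df.** Over the four unequal rows in order, three separate runs gave 13.3/11.3/8.6/8.7%, 12.6/11.1/8.0/8.1% and, with slope-plus-exponential added, 12.3/10.8/7.8/7.8%. With equal correlations the results were about 4.6% and 5.1%. Unstructured covariance gave 4.3% to 5.5% in the first run and 5.0% to 5.2% in the second.

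**5. A model of varying gain.** Score = baseline + gain × (1 − e^(−t/τ)) + residual, baseline SD 1, three visits, 300 covariance draws per case, AIC choice:

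| SD of gain | Residual SD | Type I, large df | Type I, 34 df |
|---|---|---|---|
| 0 | 0.3 | 5.7% | 5.0% |
| 0.3 | 0.3 | 7.8% | 6.8% |
| 0.6 | 0.3 | 11.2% | 10.0% |
| 0.9 | 0.3 | 13.4% | 12.1% |
| 1.0 | 0.2 | 14.8% | 13.6% |

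The two-sample change-score t test stayed at 4.9% to 5.1% in these cases. If twelve time points existed, the contrast ran from 5.1% to 10.9% on large df, and at only 6.2% to 7.2% in several strongly varying cases where AIC nearly always picked Toeplitz.

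**6. The tests the plan names.** In the four unequal rows of step 3, the 2-df arm-by-time interaction (2 and 34 df) ran at 6.6, 6.2, 5.3 and 5.3%, and the overall arm effect at 5.1% to 5.3%. A repeat gave 5.4% to 6.6% for the interaction; one run with a shorter candidate list put it at about 6% to 8%.

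**The case against.** The strongest reply is that the affected contrast is not one the plan names. The post-treatment comparison of arms belongs to the change-score test, which uses no covariance model. Within the mixed model the named test is the interaction, where the understated and overstated variances largely offset. Both points stand, and they bring the matter down from a threat to the trial's main comparison to a weakness of a supplementary analysis. A significant nominal-time interaction would, however, naturally be followed by visit-specific contrasts, and the mixed model is the only stated analysis that uses follow-up GRASSP.

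Three stronger readings are tempting, and the documents do not support them. A reader might infer that the plan's own expected course implies an inflated error rate. The sentence about early rise and later stability concerns the mean, and nominal time absorbs a common mean curve without inflation; variation in individual gains is a further assumption. A reader might infer that the non-identifiable combination causes the inflation. It does not, since its fit is that of plain Toeplitz. A reader might also infer that the trial's post-treatment test rejects about twice as often as it should. That describes only the model-based contrast, and only under some assumed SDs.

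The covariance list is also open-ended, and AIC is only a guide, so an unstructured pattern is not excluded. That is fair, but a pattern added after seeing the data is not pre-specified.

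Finally, the model as written assumes GRASSP at ten sessions where none is scheduled, and its time coding gives follow-up no value. That is a separate and more basic mismatch. The calculations here apply to the three visits that are scheduled.

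**Conclusion.** The point holds in a limited form. The redundancy of random intercept plus full Toeplitz is certain and needs no assumption, but it is a fitting defect with no effect on error rates. The inability of the named patterns to represent varying, then retained, gains is structural, given time in weeks and Toeplitz by visit order. Its consequence is conditional: at three visits and an assumed two-sided 5%, the model-based baseline-to-post arm contrast runs from about 5% with no variation in gain to about 8% to 15% with the variation assumed (the mildest varying-gain case is 6.8% on 34 df). The interaction test is at about 5% to 7%, and the change-score comparison stays near 5% if run as a two-sample test. The calculations ignore dropout, the cubic-time fit and the rule of keeping the interaction only if significant. Severity is minor to moderate because the mixed model is supplementary.

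**What to change.** In section 9, for the three scheduled GRASSP visits with nominal time, replace the candidate patterns, the random slope and the AIC step with one pre-specified unstructured within-patient covariance and no added random intercept, fitted by REML with Kenward-Roger degrees of freedom. State a fallback for non-convergence: heterogeneous compound symmetry with a robust (sandwich) variance. State also that the between-arm change-score comparison is a two-sample test.

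The cost is wording only, with no new data or visits. The downside is 3 × 4/2 = 6 covariance parameters instead of 2 to 4, estimated from 36 participants. Where correlations were equal, simulated type I error under the unstructured form stayed near 5%. The remedy depends on using three visits: at twelve time points an unstructured matrix would need 12 × 13/2 = 78 parameters, so the mismatch between the model's time points and the assessment schedule has to be settled first.
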